4.4.1.3.3 Duration

Duration will be computed using the same methodology than for unsolicited non-serious AEs described in [Section 4.4.1.2.4](#).

4.4.2 Immunogenicity

4.4.2.1 Computed Values for Analysis

In order to appropriately manage extreme values ($< \text{LLOQ}$ and $\geq \text{ULOQ}$, lower limit of quantitation and upper limit of quantitation, respectively) for analysis purposes, the following computational rule is applied to the values provided in the clinical database for each BL drawn:

- If a value is $< \text{LLOQ}$, then the computed value is $\text{LLOQ}/2$
- If a value is between $\geq \text{LLOQ}$ and $< \text{ULOQ}$, then the computed value is the value
- If a value is $\geq \text{ULOQ}$, then the computed value is ULOQ

4.4.2.2 Seroprotection

Generally, If the computed value is $\geq x$, then the derived seroprotection indicator will be "Yes" for that test, otherwise seroprotection will be "No". Note: If the computed value is missing, seroprotection will be missing.

For diphtheria, seroprotection is defined as:

- Anti-diphtheria antitoxin concentration ≥ 0.01 , ≥ 0.10 , and ≥ 1.0 IU/mL (International Unit)

For tetanus, seroprotection is defined as:

- Anti-tetanus antitoxin concentration ≥ 0.01 , ≥ 0.10 , and ≥ 1.0 IU/mL

4.4.2.3 Fold-rise

The derived endpoint fold-rise is driven by both baseline and post-baseline computed values and is computed as follows. Generally, for extreme values, this algorithm minimizes the numerator and maximizes the denominator.

- If the baseline computed value is $< \text{LLOQ}$ and the post-baseline computed value is $< \text{LLOQ}$, then the fold-rise is 1
- If the baseline computed value is $\geq \text{LLOQ}$ and the post-baseline computed value is $\geq \text{LLOQ}$, then the fold-rise is $\text{post-baseline computed value} / \text{baseline computed value}$
- If the baseline computed value is $\geq \text{LLOQ}$ and the post-baseline computed value is $< \text{LLOQ}$, then the fold-rise is $(\text{LLOQ}/2) / \text{baseline computed value}$

- If the baseline computed value is $< \text{LLOQ}$ and the post-baseline computed value is $\geq \text{LLOQ}$, then the fold-rise is post-baseline computed value /LLOQ

If the computed value is ≥ 4 , then the derived ≥ 4 -fold rises indicator will be "Yes" for that test, otherwise ≥ 4 -fold rises will be "No".

Note: If baseline or post-baseline is missing, then fold-rise is missing.

4.4.2.4 Seroconversion

Not applicable

4.4.2.5 Booster response

The criterion for demonstrating a pertussis booster response is as follows:

- If the pre-booster vaccination concentration is $< 4 \times \text{LLOQ}$, then the post-booster vaccination concentration is $\geq 4 \times$ the pre-booster concentration*
- If the pre-booster vaccination concentration is $\geq 4 \times \text{LLOQ}$, then the post-booster vaccination concentration is $\geq 2 \times$ the pre-booster concentration.

* Pre-booster vaccination concentrations $< \text{LLOQ}$ will be converted to LLOQ for purposes of calculating this booster response.

An equivalent definition for ease of programming:

- If the pre-booster vaccination concentration is missing or No Result (NR) or if the post-booster vaccination concentration is missing or NR, then the booster response is missing
- Else if the pre-booster vaccination concentration is $< 4 \times \text{LLOQ}$, then the booster response will be demonstrated if there is a 4-fold rise (post-/pre- vaccination ≥ 4)
- Else if the pre-booster vaccination concentration is $\geq 4 \times \text{LLOQ}$, then the booster response will be demonstrated if there is a 2-fold rise (post-/pre- vaccination ≥ 2)

For diphtheria and tetanus the criteria for demonstrating a booster response are as follows:

- Subjects whose pre-vaccination antibody concentrations are $< 0.1 \text{ IU/mL}$ will demonstrate the booster response if they have a post-vaccination level $\geq 0.4 \text{ IU/mL}$
- Subjects whose pre-vaccination antibody concentrations are $\geq 0.1 \text{ IU/mL}$ but $< 2.0 \text{ IU/mL}$ will demonstrate the booster response if they have a 4-fold rise (i.e., post-/pre-vaccination ≥ 4)
- Subjects whose pre-vaccination antibody concentrations are $\geq 2.0 \text{ IU/mL}$, will demonstrate the booster response if they have a 2-fold response (i.e., post-/pre-vaccination ≥ 2)

An equivalent definition for ease of programming:

- If the pre-vaccination antibody concentration is missing or No Result (NR) or if the post-booster vaccination concentration is missing or NR, then the booster response is missing
- Else if the pre-vaccination antibody concentration is < 0.1 IU/mL, then the booster response will be demonstrated if the post-vaccination level ≥ 0.4 IU/mL
- Else if 0.1 IU/mL \leq pre-vaccination antibody concentration < 2.0 IU/mL, then the booster response will be demonstrated if there is a 4-fold rise (i.e., post-/pre-vaccination ≥ 4)
- Else if the pre-vaccination antibody concentration is ≥ 2.0 IU/mL, then the booster response will be demonstrated if there is a 2-fold rise (i.e., post-/pre-vaccination ≥ 2)

4.4.3 Efficacy

Not applicable

4.4.4 Derived Other Variables

4.4.4.1 Age for Demographics

Ages of subjects will be calculated as Age (years) = (date of vaccination – date of birth +1)/365.25

4.4.4.2 Duration of a Subject in the Study

The duration of a subject in the study is computed as follows: Maximum (date of last visit, date of term form) – (date of V01) +1.

The duration of a subject in the study including follow-up is computed as follows: Maximum (date of last visit, date of term form, last date of follow-up contact) – (date of V01) +1.

4.4.4.3 Duration of the Study

The duration of the study (until last visit) is computed as follows: Maximum of all subjects (date of last visit, date of termination form) – minimum for all subjects (date of V01) +1.

The duration of the study (including follow-up) is computed as follows: Maximum of all subjects (date of last visit, date of termination form, date of last follow-up contact) – minimum for all subjects (date of V01) +1

4.4.4.4 Subject Duration

The duration of a subject participation in the study is computed as follows:

Maximum (Visit dates, Termination date, Follow-up date, Last contact date) – V01 date + 1.

4.4.4.5 MAAEs from V01 to V02

MAAEs that occur from V01 to V02 will be recorded as unsolicited AEs on the diary card as part of all unsolicited AEs collected for this post-vaccination period. The unsolicited AEs that have action taken categories 2 (health care provider contact) or 3 (Health care contact + Medication) will be summarized and presented as MAAEs which occurred from V01 to V02.

5 Statistical Methods and Determination of Sample Size

The statistical analyses will be performed under the responsibility of the Sponsor's Biostatistics platform using SAS® Version 9.4 or later.

The results of the statistical analysis will be available in the final clinical study report (CSR).

For descriptive purposes, the statistics will be presented as following:

Categorical variables: number and percentage of subjects in each category will be summarized.

Age: number of observations (n), mean, and standard deviation (SD).

The CI for the single proportion will be calculated using the exact binomial method (Clopper-Pearson method, quoted by Newcombe (2), i.e., using the inverse of the beta integral with SAS®.

For immunogenicity and efficacy results, assuming that Log10 transformation of the titers / data follows a normal distribution, at first, the mean and the 95% CI will be calculated on Log10 (titers / data) using the usual calculation for normal distribution (using Student's t distribution with n-1 degree of freedom), then antilog transformations will be applied to the results of calculations, in order to provide geometric means (GMs) and their 95% CI.

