***Unsolicited AE/AR:***

An unsolicited AE is an observed AE that does not fulfill the conditions prelisted in the CRF in terms of diagnosis and/or onset post-vaccination, i.e., excluding solicited reactions, e.g., if headache between D0 and D7 is a solicited reaction (i.e., prelisted in the CRF), then a headache starting on D7 is a solicited reaction, whereas headache starting on D8 post-vaccination is an unsolicited AE.

An unsolicited non-serious AE is an unsolicited AE excluding SAEs.

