### 9.3.1.3.2 Reactogenicity (Solicited Reactions From Day 0 to Day 7 After Vaccination)

After vaccination, subjects or subjects' parents/guardians will be provided with a safety DC, a digital thermometer, measuring tape and a flexible ruler, and will be instructed how to use them. The following items will be recorded by the subjects in the DC on the day of vaccination and for the next 7 days (i.e., D0 to D7) until resolution:

- Daily temperature, with the route by which it was taken
- Daily measurement or intensity grade of all other solicited injection site and systemic reactions
- Action taken for each event, if any (e.g., medication)

The action taken by the subject or the subject's parents/guardians to treat any **solicited reactions** will be classified in the eCRF using the following scale:

- 0: None
- 1: Medication (self-medication with an existing prescription or over-the-counter medication)
- 2: Health care provider contact (no new medication prescribed)
- 3: Health care provider contact and prescription of a new medication (health care provider instructed subject to take a new medication, either an over-the-counter medication or one requiring a written prescription)
- 4: Hospitalization (inpatient)

Subjects or subjects' parents/guardians will be contacted by telephone 8 days after vaccination to identify the occurrence of any SAE, Grade 3 solicited adverse reactions (including ELS) not yet reported and to remind them to record all safety information in the DC up to V02 and to bring the DC back to V02. The date of the appointment for V02 will be confirmed.

If the timing of the telephone call should fall on a weekend or a holiday, the call should be made on the next business day. If contact is not made on the designated day, study staff will continue calling until contact is made. Every telephone attempt and its outcome will be documented in the source document.

[Table 9.1](#) and [Table 9.2](#) present, respectively, the injection site reactions and systemic reactions that are prelisted in the DCs and CRF, together with the intensity scales.

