#### **9.3.1.3.6 Medically Attended Adverse Events**

MAAEs that occur from V01 (D0) to V02 will be recorded as unsolicited AEs on the DC as part of the unsolicited AEs collected for this post-vaccination period. MAAEs that occur from V02 to the long-term safety phone call at approximately 6 months after vaccination will be recorded as such in the MA. An MAAE that occurs within the study but meets the definition of an SAE should be reported only on the SAE reporting form.

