## 12.5 Determination of Sample Size and Power Calculation

Although there are no statistically powered hypotheses in this study, the overall study cohort (N=1350) will provide a probability of approximately 93% of observing any AE with a true incidence of 0.2%. For each formulation (N=225), there is a probability of approximately 95% of observing any AE with a true incidence of 1.3%, and a probability of approximately 36% of observing any AE with a true incidence of 0.2%.

Assuming a drop-out rate of approximately 10%, a total of 67 evaluable subjects per group is anticipated.

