An unsolicited AE is an observed AE that does not fulfill the conditions prelisted in the CRF in terms of diagnosis and/or onset post-vaccination, i.e., excluding solicited reactions, e.g., if headache between D0 and D7 is a solicited reaction (i.e., prelisted in the CRF), then a headache starting on D7 is a solicited reaction, whereas headache starting on D8 post-vaccination is an unsolicited AE.

An unsolicited non-serious AE is an unsolicited AE excluding SAEs.

Injection Site Reaction:

An injection site reaction^a is an AR at and around the injection site. Injection site reactions are commonly inflammatory reactions.

other outcomes listed in the definition above. These should also usually be considered serious. Examples of such events include allergic bronchospasm requiring intensive treatment in an emergency room or at home, blood dyscrasias or convulsions that do not result in inpatient hospitalization, or the development of drug dependency or drug abuse, new onset diabetes, or autoimmune disease.

^a All injection site AEs are considered to be related to vaccination and are therefore all *injection site reactions*.

Systemic AE:

Systemic AEs are all AEs that are not injection site reactions. They therefore include systemic manifestations such as headache, fever, as well as localized or topical manifestations that are not associated with the vaccination site, e.g., erythema that is localized but that is not at the injection site.

Medically Attended Adverse Events (MAAEs)

An MAAE is defined, for the purpose of this study, as a new onset of a condition that prompts the subject or subject's parent/guardian to seek unplanned medical advice at a physician's office or Emergency Department. This definition excludes pre-planned medical office visits for routine pediatric check-ups or follow-up visits of chronic conditions with an onset prior to entry in the study. Physician contact made over the phone or by email will be considered a physician office visit for the purpose of MAAE collection.

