4.3.1.3.2 Reactogenicity (Solicited Reactions From Day 0 to Day 7 After Vaccination)

After vaccination, subjects or subjects' parents/guardians will be provided with a safety DC, a digital thermometer, measuring tape and a flexible ruler, and will be instructed how to use them. The following items will be recorded by the subjects in the DC on the day of vaccination and for the next 7 days (i.e., D0 to D7) until resolution:

- Daily temperature, with the route by which it was taken
- Daily measurement or intensity grade of all other solicited injection site and systemic reactions
- Action taken for each event, if any (e.g., medication)

The action taken by the subject or the subject's parents/guardians to treat any **solicited reactions** will be classified in the eCRF using the following scale:

- 0: None
- 1: Medication (self-medication with an existing prescription or over-the-counter medication)
- 2: Health care provider contact (no new medication prescribed)
- 3: Health care provider contact and prescription of a new medication (health care provider instructed subject to take a new medication, either an over-the-counter medication or one requiring a written prescription)
- 4: Hospitalization (inpatient)

Subjects or subjects' parents/guardians will be contacted by telephone 8 days after vaccination to identify the occurrence of any SAE, Grade 3 solicited adverse reactions (including ELS) not yet reported and to remind them to record all safety information in the DC up to V02 and to bring the DC back to V02. The date of the appointment for V02 will be confirmed.

If the timing of the telephone call should fall on a weekend or a holiday, the call should be made on the next business day. If contact is not made on the designated day, study staff will continue calling until contact is made. Every telephone attempt and its outcome will be documented in the source document.

Table 4.1 and Table 4.2 present, respectively, the injection site reactions and systemic reactions that are prelisted in the DCs and CRF, together with the intensity scales.

Table 4.1: Solicited injection site reactions : terminology, definitions, and intensity scales

CRF term (MedDRA lowest level term [LLT])	Injection site pain	Injection site erythema	Injection site swelling	Upper limb edema	Extensive swelling of the vaccinated limb
Diary card term	Pain*	Redness*	Swelling*	Change in limb circumference*	Extensive limb swelling*

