SAE	Up to 7 days after D0 for all subjects in Groups 1 – 6 From D0 to D30 for all subjects in Groups 1 – 6 From D31 to 6-month follow-up contact for all subjects in Groups 1 – 6 Up to 6-month follow-up contact after D0 for all subjects in Groups 1 – 6	Percentage of subjects that have the event, MedDRA terms, time of onset, duration, relationship, seriousness criteria, outcome, study discontinuation
MAAE	From V01 to V02 for all subjects in Groups 1 - 6 (as unsolicited AE) From V02 to 6-month follow-up contact for all subjects in Groups 1 - 6	Percentage of subjects that have the event, MedDRA terms, time of onset, duration, intensity, relationship, action taken, outcome, study discontinuation

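### The V01–V02 MAAE row (SAP 4.4.4.5, Table 5.1) counts unsolicited AEs only, so non-serious solicited reactions that meet the plan's own MAAE definition are left out

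*SAP*

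**What the plan says.** **Definition.** Protocol 9.3.1.1 and SAP 4.3.1.1 define an MAAE "as a new onset of a condition that prompts the subject" or a parent or guardian to look for unplanned medical advice at a doctor's office or emergency department. Phone and email contact count. The only exclusions are pre-planned visits for routine check-ups or for follow-up of chronic conditions that began before entry.

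**Solicited versus unsolicited.** The same sections make the two classes mutually exclusive: "a headache starting on D7 is a solicited reaction, whereas headache starting on D8 post-vaccination is an unsolicited AE".

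**Routing.** Protocol 9.3.1.3.6 states that "MAAEs that occur from V01 (D0) to V02 will be recorded as unsolicited AEs on the DC". SAP 4.4.4.5 turns this into a derivation: "The unsolicited AEs that have action taken categories 2 (health care provider contact) or 3 (Health care contact + Medication) will be summarized" and presented as the MAAEs of that period. The MAAE row of SAP Table 5.1 reads "From V01 to V02 for all subjects in Groups 1 - 6 (as unsolicited AE".

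**Action codes.** For solicited reactions, Protocol 9.3.1.3.2 classifies "The action taken by the subject or the subject's parents/guardians to treat any" such reaction on a scale that includes "2: Health care provider contact (no new medication prescribed" (SAP 4.3.1.3.2) and a code 3 for provider contact with a new medication. These are the codes that SAP 4.4.4.5 uses for unsolicited AEs.

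**Serious events.** An MAAE that is also an SAE is reported only as an SAE, so the point concerns non-serious events.

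**The concern.** The derivation is narrower than the definition that it is meant to implement. Protocol 1.3.2 names injection site reactions, fever and extensive limb swelling (ELS) as the expected risks, and these are solicited terms. When one of them sends a subject to a doctor in the first week, the V01–V02 MAAE row does not show it.

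Table 5.1 reports MAAEs by relationship, and all solicited reactions are related by convention (SAP 4.3.1.3.7). The omission therefore also lowers the related count in that row.

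The row is the only MAAE output in the preliminary analysis of V01–V02 data announced in SAP 5.7. Safety data are to inform the choice of formulation (Protocol 1.4). A reader who takes the row at face value would believe that it gives the number of subjects with any medically attended event in the period, which it does not.

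**Working it through.** No formula decides this point; it follows from setting the rules side by side.

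1. Take a non-serious headache that starts on D3 and leads the subject to phone a doctor, unplanned. It is a new-onset condition, the phone call counts as an office visit, and neither exclusion applies. It is an MAAE under SAP 4.3.1.1.
2. Headache with onset on D0–D7 is prelisted, so it is a solicited reaction and by definition not an unsolicited AE.
3. Its action code (2, or 3 if a new medication is prescribed) is recorded on the solicited scale.
4. SAP 4.4.4.5 and Table 5.1 draw only on unsolicited AEs. The event is not counted.
5. No section of either document tells sites to enter such a reaction a second time as unsolicited.

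**Direction.** The omission in step 4 lowers the count. The row also has a leak the other way. The AE definition includes worsening of a pre-existing condition, which is not new onset. Codes 2 and 3 record provider contact without asking whether it was unplanned or where it took place (SAP 4.3.1.3.3). Some unsolicited AEs in the row may therefore not be MAAEs. The net direction cannot be derived.

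**Size.** The documents give no rate of solicited reactions leading to provider contact. Only scale can be shown.

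- Inputs: 225 subjects per formulation (Protocol 12.5) and 75 per age group within a formulation (Synopsis, Table S2).
- The plan's own figure: P(at least one) = 1 − (1 − p)^n. With p = 1.3% and n = 225, 1 − 0.987^225 = 94.7%; the plan says about 95%. This confirms the formula. It says nothing about how often the omission occurs.
- One omitted subject with no other counted event moves the rate by 1/225 = 0.44 points per formulation, or 1/75 = 1.33 points in an age group.
- Assumption, for range only: between 0.5% and 5% of subjects have a non-serious solicited reaction as their only medically attended event in V01–V02.

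| Assumed p | n | Expected omitted (n × p) | P(at least one) |
|---|---|---|---|
| 0.5% | 225 | 1.1 | 68% |
| 5% | 225 | 11.3 | nearly 100% |
| 0.5% | 75 | 0.4 | 31% |
| 5% | 75 | 3.8 | 98% |

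These subjects have no other counted event, so a combined rate would exceed the planned row by p itself: 0.5 to 5 points. Subjects who also have a counted unsolicited event add nothing.

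**The case against.** **The plan may intend these events to be entered as unsolicited.** Protocol 9.3.1.3.6 says without exception that V01–V02 MAAEs are recorded that way. If that covers solicited terms, SAP 4.4.4.5 would capture them. This reading contradicts the definition of an unsolicited AE, would put solicited reactions into the unsolicited tables, and has no instruction for a second entry behind it. It does not stand, but it shows that the conflict starts in the protocol and that the SAP inherits it.

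**MAAE in this window may mean a subset of unsolicited AEs.** Protocol 12.1.2 does list MAAEs within unsolicited AEs, and Table 5.1 discloses the source. It is true that the routing is consistent and open. The definition, however, carries no such limit, so the label and the definition still disagree.

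**Nothing is lost and no decision depends on the row.** This largely stands. Action taken for solicited reactions has its own line in Table 5.1, the MAAE endpoint in SAP 4.3.1.2 starts at V02, no hypotheses are tested (SAP 5.1.3.1), and neither alert threshold of the early safety data review uses MAAEs. What the separate tables cannot give is the number of subjects with any medically attended event, because the overlap between them is unknown.

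**A combined row would bring in contacts that the protocol itself requires.** This stands as a caution. Sites must try to see subjects with Grade 3 reactions or ELS within 24 hours (Protocol 5.1.4), and no section says how that visit is coded. Dropping all solicited reactions with code 2 and Grade 3 would not solve this: it would remove genuine physician contacts and keep code 3 cases from the same required visit.

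**Conclusion.** The mismatch is real and follows from the text. The V01–V02 MAAE row omits non-serious solicited reactions that meet the MAAE definition, and the protocol's routing sentence has the same conflict. It rests on reading the definition of an unsolicited AE as written.

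A reader might infer that the row can only understate MAAEs. The documents do not support that: the omission lowers the count, but codes 2 and 3 may also admit events that are not MAAEs, so the net direction is unknown. A reader might also infer that the MAAE endpoint or the early safety review is compromised. The endpoint window begins after this period, and the review lists solicited reactions as a parameter of their own.

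The size is unknown. The 0.5% to 5% range is an assumption with no support in the documents. This is a worthwhile, inexpensive correction to one descriptive row.

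**What to change.** In SAP 4.4.4.5 and the MAAE row of Table 5.1:

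- Keep the planned row and label it as unsolicited MAAEs.
- Add a row for non-serious solicited reactions with action code 2 or 3, marked as related by convention. Split it by maximum intensity (Grade 3 versus lower) of the reactions carrying those codes. The triggers for a required site assessment (Grade 3 reaction, an increase of at least 50 mm in arm circumference, ELS) all derive to Grade 3 under SAP Table 4.1 and 4.4.1.1.1. The split shows where such contacts can lie without claiming to separate them from genuine ones.
- Add a combined row giving only the number and percentage of subjects, each counted once. Relationship and outcome stay out of it, since the solicited output does not carry the same content.
- Footnote that codes 2 and 3 are a proxy for the definition: they test neither new onset nor unplanned contact, and may include protocol-driven site assessments.

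Record the change in SAP 5.7. If only the wording can change, the minimum is the label plus a pointer to the solicited action-taken output; that removes the ambiguity but does not supply the subject-level count.

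The cost is SAP wording and a modest amount of programming from codes and grades already collected. The combined rate will be at least as high as the planned row and may include some protocol-driven contacts. Nothing changes in data collection or in the handling of subjects.
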